Protocol Clinical Trial

Title of the project

Tight caloric control (TiCaCO) in the cachectic oncologic patient before the start of cancer therapy can stabilize body weight, thereby reducing morbidity and mortality: validation of the pilot trial. A randomized study.

Objective of the study

In our pilot trial, 20 patients were randomized, 10 receiving regular counseling by regular oncodietitians, while the 10 others received nutrition therapy. In the latter group, an assessment of biophysical parameters was made (including the bioelectrical impedance analysis or BIA for body composition), and their Energy Expenditure was assessed using indirect calorimetry. Afterwards, they received nutrition therapy according to the ESPEN (European Society for Parenteral and Enteral Nutrition) guidelines. Supplementary interventions were made to match caloric intake to energy expenditure (the 'Tight Caloric' approach), using enteral and parenteral nutrition if indicated, by an intensive coaching and follow-up to continue this nutrition strategy (with dieticians even being "on call" after hours). While the study follow-up lasted 2 years, nutrition therapy was only performed during the first 3 months. The results were striking: apart from keeping their body weight in balance, the patients of the nutrition therapy group counted much less unexpected hospitalisation days and they clearly lived much longer (De Waele, Appetite, 2015).

This project targets the validation of these results on a large scale. For this study, patients with either colorectal adenocarcinoma and non-small cell lung carcinoma, due to their high incidence as well as the high prevalence of cachexia in these patients will be included. While patients will be randomized, it is not possible to perform a double- or even single-blinded study due to the nature of the treatment. The recruitment phase will last 2 years, keeping refusals and dropouts in mind. Follow-up will last 2 years after inclusion, although the actual nutrition therapy will again last only 3 months: the period of active oncological treatment. An intermediate analysis is already made after the first year of follow-up. In case survival is already statistically significant, the trial will be stopped for ethical reasons. In case of a positive result, we want to implement nutrition therapy as a standard treatment in cachectic cancer patients in Belgium.

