Study design

randomized controlled double-blind parallel-group multi-centre study

Medication/device *If applicable*

Not applicable (enteral and parenteral nutrition, commercially available)

The subjects

Number of subjects

- Colorectal cancer (CRC) st. III - IV (TNM system) with cachexia
- Non-small cell lung cancer (NSCLC) st. III - IV (TNM system) with cachexia

120 subjects in each group, 60 controls and 60 Nutrition Therapy patients, based on statistical power. 20% extra patients were added to this number to account for dropouts.

Investigational group (Group A)

At the time of diagnosis, patients will immediately be screened and started with Nutrition Therapy if assigned to group A. This regimen will stay in place for 3 months, after which a switch will be made towards normal dietary counselling. Nutrition Therapy can be given orally, parenterally or via tube feeding, depending on the patient's status and aims at matching caloric Intake with Resting Energy Expenditure. Moreover, a switch between these modalities is possible during these 3 months. Afterwards, standard dietary counselling will be given during the remainder of the study. Follow-up will last 1 year. If one year after the last enrolment the study shows a large difference with the control group, the study will be stopped for ethical reasons.

Reference group (Group B)

At the time of diagnosis, patients will immediately be screened and started with standard dietary counselling for 2 years if assigned to group B. Dietary intervention can be orally, parenterally or via tube feeding, depending on the patient's status. Moreover, a switch between these modalities is possible during these 3 months. Follow-up will last 1 year. If one year after the last enrolment the study shows a large difference with the control group, the study will be stopped for ethical reasons.

Both Groups:

Oncological treatment will be performed at the discretion of the participating specialists, following the ESMO guidelines. Although an open label study, the oncologic treatment will not be related to the dietary regimens.

Inclusion is to take place in a period of one year. The duration of the study for each subject from randomisation to end of treatment is three months and a follow up period of nine months, for a total of one year per patient. Afterwards, analysis will take place.

Power calculation:

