96 patients per cancer group (48 controls and 48 nutrition therapy), supplemented with 20% per group to take dropouts into account.

Inclusion criteria

- > 18 years
- Male and female
- CRC or NSCLC before chemo- or radiotherapy is started (naive to treatment), but surgery may already have been performed
- CRC or NSCLC relapse > 3 months after initial oncologic therapy
- Oncologic cachexia (undesired weight loss > 5% in less than 6 months)
- Written informed consent / ability to give informed consent

Exclusion criteria

- concomitant second malignancy
- uncertainty of diagnosis of CRC or NSCLC
- patient unfit for chemotherapy
- patient unfit for radiotherapy
- patient unfit for surgery
- palliative treatment or terminal patient (life expectancy < 3 months)
- patient already participating in another study
- Pregnancy / lactation
- Any other pathology present that causes the patient to be unfit for oncologic therapy (e.g. end-stage renal failure, severe COLD, severe heart failure)
- Unable to adhere to protocol instructions (e.g. language barrier)
- Investigator's uncertainty about the willingness or ability of the patient to comply with the protocol requirements
- Participation in any other studies involving investigational or marketed products concomitantly or within two weeks prior to entry into the study

Replacement of subjects

In case of dropout, subjects will be censored on the Kaplan-Meier curves.

[figure not shown]
Restrictions and prohibitions for the subjects

None.

Procedures

See below, to be performed at the oncology consultation.

Flowchart

systematic overview of the study: planned tests per visit of the subjects

Expected total duration of the trial: 2 year (inclusion).

Supervising MD during the tests: Principal Investigator: [name] or co-investigator: [name].

Randomisation/blinding

Computerized randomization, validated for clinical trials, are used.

Prior and concomitant therapy

See "Inclusion and Exclusion criteria". All other concomitant therapy is allowed.

Study analysis

Sample size calculation

The statistical power was calculated based on the pilot trial.

Analysis of the samples

Outcome parameters:

• Body weight
• BIA Bio-Electrical Impedance Analysis
• Blood Pressure
• Blood Sample Analysis
• Caloric and Nitrogen intake
• Indirect Calorimetry
• Sensewear ®
• Body weight
• BIA Bio-Electrical Impedance Analysis
• Blood Pressure
• Blood Sample Analysis
• Indirect Calorimetry
• Body weight, mortality, morbidity.

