- Primary: weight stabilisation, morbidity and mortality
- Secondary: Quality of Life (QoL 36)

Statistical analysis

2-tailed, paired t-tests will be used for statistical analysis.

Quality control and quality assurance

The quality control is performed by the certified and experienced research unit of the Intensive Care Department.

Publication policy

All rights belong to the PI and thus to the VUB/the UZ Brussel.

Protocol Amendment dd 12/06/2017

Background:

Due to lack of patients with 5% weight loss in 6 months and, by consequence, very low inclusion rate, it was decided to amend the protocol. To achieve this, a special cooperation with the department of Radiotherapy was established. The service sees many patients who lose weight during radiotherapy, partly because of cancer-related cachexia, but mostly due to the mucositis caused by radiotherapy itself, losing > 10% of their initial body weight (at the start of their therapy). This is especially seen in cancers of head and neck, oesophagus and stomach. Radiotherapy is performed on working days and treatments typically last 5-7 weeks (depending on indication).

Amendment:

- Inclusion of patients with colorectal, lung and pancreatic cancer will be changed to: Inclusion of patients with lung, gastric, oesophageal, head and neck and pancreatic cancer
- 5% weight loss over the past 6 months will be changed to: patients with the aforementioned cancers where radiotherapy will be part of their treatment (or will be the entire treatment)
- Duration of intervention of 3 months will be changed to: duration of intervention for the entire period of radiotherapy
- After recalculation of statistical power, only 48 patients will be needed instead of 96. With correction for dropouts, this will become 60 patients instead of 120. This means 30 controls and 30 patients in the intervention group.
- The amendment will be added to the registration at *clinicaltrials.gov*.

The procedure and flowchart will remain unchanged. Analysis of the data will remain: in whole, per cancer and per sex (the latter two criteria requiring 60 patients in each group).

Protocol Amendment dd 19/09/2017

Background:

The study has seen much more inclusions and is running well thanks to the previous amendment. Due to a typo, the colorectal cancer group was unfortunately omitted. Also, the absolute difference of survival in the TiCaCo trial after one year was similar to that after the second year.

Amendment:

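### The only test the protocol names, a paired t-test, does not fit two unmatched randomised arms or a censored mortality outcome

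*Protocol*

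**What the plan says.** The Statistical analysis section of the protocol consists of one sentence: "2-tailed, paired t-tests will be used for statistical analysis". It is not limited to any outcome, and no other hypothesis test is named in the protocol.

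The rest of the protocol describes a different structure:

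- **Design.** Study design calls the trial a "randomized controlled double-blind parallel-group multi-centre study", with an investigational Group A and a reference Group B. Only the parallel-group part of that label matters here.
- **Allocation.** Under Randomisation/blinding: "Computerized randomization, validated for clinical trials, are used". No section describes matched pairs, crossover or any other link between a patient in one arm and a patient in the other.
- **Outcomes.** The outcome list gives "Primary: weight stabilisation, morbidity and mortality".
- **Dropouts.** Under Replacement of subjects: "In case of dropout, subjects will be censored on the Kaplan-Meier curves".
- **Interim look.** The Objective and the Rationale both refer to a significance result on survival: "In case survival is already statistically significant, the trial will be stopped for ethical reasons".
- **Size.** The power calculation gave "96 patients per cancer group (48 controls and 48 nutrition therapy), supplemented with 20% per group to take dropouts into account". The amendment of 12/06/2017 reduced this: "After recalculation of statistical power, only 48 patients will be needed instead of 96". It sets 60 patients including dropouts, 30 per arm.

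None of the three amendments changes the test. The first says only that the data will still be analysed overall, by cancer and by sex.

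**The concern.** A paired t-test needs a natural pair for each observation. In a parallel-group trial without matching, the only natural pairs are two measurements on the same patient. A test on those pairs asks whether weight changed over time in one arm. It does not ask whether nutrition therapy changed weight relative to control, which is the question that randomisation was set up to answer.

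Two things are at stake. For weight, two separate within-arm tests could be read side by side, and a significant loss in one arm with a non-significant change in the other could be taken as stabilisation. That pattern can arise by chance when the arms do not differ. For mortality, a paired t-test does not apply: a death has no before-and-after pair, and censored follow-up cannot enter a t-test. Yet early stopping depends on a survival result being statistically significant.

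**Working it through.** **Inputs from the protocol.** 48 evaluable patients after the 2017 amendment, allocated 1:1, so 48/2 = 24 per arm. The dropout step reproduces: 48/(1 − 0.20) = 60, as stated, and for the original plan 96/(1 − 0.20) = 120, as stated. The 48 and 96 themselves cannot be reproduced, because no effect size, SD, event rate, alpha or power is given.

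**Assumptions.** Two-sided alpha of 0.05; normally distributed weight change; a true mean change of δ, in units of the SD of within-patient change, that is the same in both arms, so that there is no treatment effect.

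**Reading 1: a before/after test within each arm.** With n = 24 the test has 23 degrees of freedom, critical value 2.069 and noncentrality δ√24. Let p be the probability that one arm is significant. The arms are independent, so

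- P(control significant, nutrition not) = p(1 − p)
- P(exactly one arm significant) = 2p(1 − p)

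| δ (SD) | p | control only: p(1 − p) | exactly one: 2p(1 − p) |
|---|---|---|---|
| 0 | 5.0% | 4.8% | 9.5% |
| 0.2 | 15.6% | 13.1% | 26.3% |
| 0.3 | 29.1% | 20.6% | 41.3% |
| 0.42 | 50.5% | 25.0% | 50.0% |
| 0.5 | 65.0% | 22.7% | 45.5% |
| 0.6 | 80.4% | 15.8% | 31.6% |
| 0.8 | 96.3% | 3.5% | 7.1% |
| 1.0 | 99.7% | 0.3% | 0.6% |

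The product p(1 − p) cannot exceed 0.25 and reaches it at p = 0.5. The 25% is therefore a mathematical ceiling, met at a change near 0.42 SD, and not an estimate for this trial.

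**Reading 2: patients paired arbitrarily across arms.** With independent arms, the test keeps about the right type I error. Its degrees of freedom are n − 1 = 23 instead of 2n − 2 = 46. For a true difference of 0.8 SD the noncentrality is 0.8 × √(24/2) = 2.77 in both cases:

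- unpaired, 46 df (critical value 2.013): power 77.4%
- arbitrary pairs, 23 df (critical value 2.069): power 75.6%

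The loss is 77.4 − 75.6 = 1.8 points. The larger objections are that nothing in the design says who is paired with whom, so the result depends on an arbitrary choice, and that a dropout removes the partner as well. The amendment of 05/02/2019 reports that there are too many dropouts.

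**Mortality.** No arithmetic is needed. The protocol censors dropouts on Kaplan-Meier curves and refers to survival being significant, so it intends a time-to-event analysis. A Kaplan-Meier curve is an estimate and not a test between arms, and the one test that is named cannot use censored times.

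**The case against.** The strongest reply is that the word paired may be a slip for unpaired. The protocol frames its result as a difference from the control group, which is a between-arm contrast, and if the word is a slip, one changed word would repair the analysis of weight. That may be so, but a reader cannot tell from the text, three amendments left the sentence alone, and an unpaired t-test would still not handle censored mortality.

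A second reply is that naming a log-rank test or Cox model is commonly left to the SAP, which is not shown. This stands in part. Silence on the survival test would be no fault. The fault is that the protocol states a general rule that does not fit the outcome.

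Three stronger readings are tempting, and the documents do not support them:

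- A reader might infer that the trial would declare stabilisation because one arm changed significantly and the other did not. No section states that decision rule. It is only a possible use of the named test.
- A reader might take 25% as this trial's false-positive rate. The protocol gives no SD of weight change, so the size of the common change in SD units is unknown. The background to the first amendment mentions losses above 10% of body weight during radiotherapy. If that is large relative to the SD, the rate is far lower: 3.5% at 0.8 SD and 0.3% at 1.0 SD.
- A reader might call arbitrary cross-arm pairing invalid. Its size is about right and its power loss is small. It is better described as without basis in the design and wasteful when patients drop out.

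**Conclusion.** The sentence is wrong as written and needs correcting. It names a test for paired data in a trial of independent, unmatched arms, and it does not fit a primary outcome that the same protocol treats as censored survival. This is a stated rule that conflicts with the design, not a detail left for later, and an SAP that departs from it would still leave the protocol to be corrected.

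The numerical consequence is limited and depends on assumptions. With 24 per arm, two-sided 5% tests and no difference between arms, the misleading pattern for weight ranges from 0.3% to a ceiling of 25% over common changes of 0.2 to 1.0 SD. The documents do not say where in that range this trial would fall. For mortality there is no figure to give: the named test cannot be used at all.

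**What to change.** Replace the sentence with between-arm tests on all randomised patients, one for each primary outcome:

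- **Weight:** compare the arms by ANCOVA adjusted for baseline weight. An unpaired t-test on change from baseline is the minimum.
- **Mortality:** a two-sided log-rank test with a Cox hazard ratio, consistent with the Kaplan-Meier curves already planned.
- **Morbidity:** a two-sample test suited to how morbidity is defined. The protocol does not define it, so the definition has to be written first.

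Within-arm changes may still be reported descriptively. Adjusting or stratifying by tumour-site group is optional and not needed to correct the error; with about 48 evaluable patients it is open to debate.

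The cost is one paragraph of wording. No new data are needed, since body weight and mortality are already on the outcome list.

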In case of a positive outcome (i.e. mere confirmation of our published results), the major advantage of nutrition therapy will be its relatively low cost while still affecting morbidity and mortality significantly. This can be practically achieved by redefining the dietician's task. The patient's own active participation in the decision making process is an important surplus in well-being and overall treatment. In combination with decreased morbidity and mortality the benefit of the patient can be found on every level.

Investigator(s)

PI and head of department of nutrition:

[name] [name], PhD: [contact]

Intensive Care UZ Brussel

Co-investigator:
[name], PhD: [contact]
Diabetes Clinic UZ Brussel

Sponsor *If applicable*

Baxter
Nutricia

Departments/laboratories involved in the study
Department of Nutrition: [contact]
Department of Intensive Care:
[contact] or [contact]
Department of Oncology: [contact]

Introduction

Background

Cancer is a disease with a high prevalence and incidence worldwide, and often incurable because the diagnosis is made in an advanced stadium. Nevertheless, 50% of patients survive on average 10 years nowadays (accounting for all cancers together). This, however, does not necessarily equals a state of being cured from cancer. On the other end of the spectrum there are patients with a very poor prognosis from the beginning, regardless of treatment. The financial drawback is that the costs for treating cancer worldwide are the highest of any disease, accounting for nearly one trillion euro per year.

One major cause for a poor prognosis is the presence of malnutrition, due to a decreased intake, caused by the patient's symptoms. Symptoms can vary greatly, but are usually of gastrointestinal nature (nausea, vomiting), although general weakness and even depression can be present, all caused by advanced disease itself or by therapy (typically chemotherapy). Advanced disease is also marked by an increased resting energy expenditure, due to the tumor's induction of a hyperkatabolic state of the body. This will cause the clinical entity called "cachexia" and will eventually be responsible for the patient's demise. Although cachexia is usually referred to as a body mass index (BMI) of < 20, in cancer a broader definition is used, whereby a weight loss > 5% over a period of 6 months is sufficient for the diagnosis, regardless of BMI (Fearon K, Nature Reviews Clinical Oncology, 2013).

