In our pilot trial, 20 patients were randomized, 10 receiving regular counseling by regular oncodietitians, while the 10 others received nutrition therapy. In the latter group, an assessment of biophysical parameters was made (including the bioelectrical impedance analysis or BIA for body composition), and their caloric status was assessed using indirect calorimetry. Afterwards, they received nutrition therapy according to the ESPEN (European Society for Parenteral and Enteral Nutrition) guidelines and supplementary matching caloric intake to energy expenditure (the 'Tight Caloric' approach) by an intensive coaching and follow-up to continue this nutrition strategy (with dieticians even being "on call" after hours). While the study follow-up lasted 2 years, nutrition therapy was only performed during the first 3 months. The results were striking: apart from keeping their body weight in balance, the patients of the nutrition therapy group counted much less unexpected hospitalisation days and they clearly lived much longer (De Waele, Appetite, 2015).

This project targets the validation of these results on a large scale. For this study, patients with either colorectal adenocarcinoma and non-small cell lung carcinoma, due to their high incidence as well as the high prevalence of cachexia in these patients. While patients will be randomized, it is not possible to perform a double- or even single-blinded due to the nature of the treatment. The recruitment phase will last 2 years, keeping refusals and dropouts in mind. Follow-up will last 2 years after inclusion, although the actual nutrition therapy will again last only 3 months. An intermediate analysis is already made after the first year of follow-up. In case survival is already statistically significant, the trial will be stopped for ethical reasons. In case of a positive results, we want to implement nutrition therapy as a standard treatment in cachectic cancer patients in Belgium.

In case of a positive outcome (i.e. mere confirmation of our published results), the major advantage of nutrition therapy will be its relatively low cost while still affecting morbidity and mortality significantly. This can be practically achieved by redefining the dietician's task. The patient's own active participation in the decision making process is an important surplus in well-being and overall treatment. In combination with decreased morbidity and mortality the benefit of the patient can be found on every level.

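### The June 2017 amendment removed cachexia as the entry criterion, but the title, pilot-validation objective and planned conclusion still concern cachectic patients, whom the trial no longer selects for

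*Protocol*

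**What the plan says.** **Target population.** The Protocol's Title of the project concerns tight caloric control "in the cachectic oncologic patient before the start of cancer therapy can stabilize body weight" and calls the trial a validation of the pilot. Objective of the study then gives the intended use of the result: "In case of a positive result, we want to implement nutrition therapy as a standard treatment in cachectic cancer patients in Belgium". The Rationale repeats it almost word for word.

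**Definition.** The Background section of the Introduction says that in cancer "a weight loss > 5% over a period of 6 months is sufficient for the diagnosis, regardless of BMI". The Inclusion criteria list made this a condition of entry.

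**Change.** Protocol Amendment dd 12/06/2017 gives a shortage of patients with that weight loss as its reason and says: "5% weight loss over the past 6 months will be changed to: patients with the aforementioned cancers where radiotherapy will be part" or the whole of treatment. It also replaces the 3-month intervention by one lasting for the period of radiotherapy, which it describes as typically 5-7 weeks. It attributes weight loss in the new patients partly to cancer cachexia but "mostly due to the mucositis caused by radiotherapy itself".

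**Analysis sets.** The same amendment keeps the analysis as whole, per cancer and per sex.

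**Later amendments.** The amendment of 19/09/2017 restores colorectal cancer, leaves the other entry criteria alone and shortens follow-up. That of 05/02/2019 deals with the inclusion period and number. None of the three touches the title, objective or intended conclusion.

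**The concern.** Entry was changed from weight loss that has already happened to a treatment during which weight loss is expected. By the protocol's own account, the main cause of that loss is also different. The amended trial therefore mainly asks whether nutrition therapy limits weight loss during radiotherapy. The question in the title and objective is whether it helps patients who are already cachectic.

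The stated purpose is a change of standard care for cachectic patients. If the plan is followed as written, a positive pooled result in patients not selected for cachexia would be used to justify that change, even though the effect might come mainly from patients who were not cachectic at entry. A null pooled result would be just as hard to read for cachexia. None of the stated analysis sets would show which situation applies.

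**Working it through.** **1. Passages side by side**

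| Element | Body of the Protocol | After the 12/06/2017 amendment |
|---|---|---|
| Entry | >5% undesired weight loss in under 6 months | Listed cancer with radiotherapy as part or all of treatment |
| Intervention period | 3 months | Period of radiotherapy, typically 5-7 weeks |
| Source of weight loss | Cachexia | Mostly mucositis, partly cachexia |
| Title, pilot validation, intended practice change | Cachectic patients | Not changed |
| Analysis sets | – | Whole, per cancer, per sex |

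The criterion that was replaced is the one that defines cachexia in the Background, so the amendment removes cachexia as a requirement by the protocol's own definition. Taking 3 months as about 13 weeks, the new period is 5/13 = 0.38 to 7/13 = 0.54 of the old one. Population and intervention period both changed, while the validation aim did not.

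**2. The plan's own figures**

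Inputs: 48 and 96 evaluable (12/06/2017 amendment) and a 20% dropout allowance (Number of subjects; Power calculation). With N/(1 − d):

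- 48/(1 − 0.20) = 60, as stated.
- 96/(1 − 0.20) = 120, as stated.

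The 48 and 96 cannot themselves be re-derived, because the Protocol gives no effect size, SD, event rate, alpha or power.

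**3. How many patients could bear on the cachexia claim**

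The cachectic share is not in the Protocol. The shares below are assumptions that span a wide range, and 48 is taken as the trial total.

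For scale, suppose 24 per arm gives 80% power at two-sided 5% (also an assumption). By the normal approximation the standardised effect is (1.96 + 0.84) × √(2/24) = 0.81. With share s cachectic, equally in both arms, power in that subset is Φ(0.81 × √(24s/2) − 1.96), computed with unrounded values.

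| Share s | Cachectic among 48 | Power in that subset |
|---|---|---|
| 10% | 4.8, about 5 | 14% |
| 25% | 12 | 29% |
| 50% | 24 | 51% |
| 75% | 36 | 68% |

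Under these assumptions the subset falls short of 80% power at every share shown, and the shortfall is large at the lower shares. The normal approximation is crude for the smallest rows, so the table shows order of magnitude only.

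**The case against.** **Is this only a difference from superseded text?** No. The amendments are appended to a body that was not rewritten and are the only source of the current entry criteria. The title and intended conclusion are still in force.

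**The intention is not a decision rule.** This is fair. The sentence on Belgian practice states a wish; it is not an endpoint or a test. The randomised comparison is not damaged, and the repair is mainly one of wording.

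**The evidence is not irrelevant to cachexia.** This also stands. The definition of cachexia names no cause, and the amendment describes patients losing more than 10% of body weight during radiotherapy, so some could meet the definition while on study. That is still not cachexia at entry, but it makes the evidence indirect rather than absent. It would go too far to say that the trial can contribute nothing to validating the pilot.

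A reader might infer several stronger points, which the Protocol does not support:

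- *Cachectic patients are not enrolled.* They are no longer required, but they are not excluded, and patients entered under the original criteria all had to meet the weight-loss criterion.
- *Few enrolled patients are cachectic.* The shortage arose under the earlier criteria. The amendment adds gastric, oesophageal and head and neck cancers and a new cooperation with radiotherapy, and nothing shows how common prior weight loss is there.
- *Entry no longer precedes cancer therapy.* Only the title makes that point. The treatment-naive criterion was not expressly withdrawn, and the original 3 months were already described as the period of active oncological treatment.
- *Prior weight loss is not recorded.* The flowchart is not shown, so this cannot be said.
- *Pooling across eras distorts the result materially.* The number of pre-amendment patients is unknown. Inclusion is described as very low, so the effect may be small.

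**Conclusion.** The point holds as a mismatch between the amended entry criteria and the unamended title, validation aim and intended conclusion. The textual mismatch is certain, since each element is explicit and no later amendment repairs it.

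Its size is uncertain. The 5-to-36 range and the power figures rest on assumed shares and an assumed 80% power, and show only that the part of the trial bearing directly on cachexia could be small. What can be said without assumption is that the stated conclusion does not follow from the pooled comparison as planned, and that the stated analysis sets offer no way to recover it. The change should be made, although the trial's comparison in the patients actually enrolled remains valid for those patients.

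**What to change.** 1. Restate the title, objective and planned conclusion for the enrolled population: patients with the listed cancers receiving radiotherapy.
2. Drop the practice claim for cachectic patients, or make it conditional on results in patients with more than 5% weight loss in the 6 months before entry.
3. Report those patients, and the patients entered before the June 2017 amendment, as a named descriptive subgroup with its limited precision stated. Use baseline weight history for this, and record it if it is not already collected.

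The cost is an amendment, matching registry wording and possibly one baseline history item. Sample size is unaffected. The downside is a narrower claim.
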